11.1 Ethics committee vote	29
11.2 Official registration	29
11.3 Insurance	29
11.4 Patient information and informed consent	29
11.5 Declaration of Helsinki	29
11.6 Data protection	29
12 DATA AND QUALITY MANAGEMENT	30
12.1 Patient identification list	30
12.2 Documentation forms	30
12.3 Monitoring	30
12.4 Direct access to source data / documents	30
12.5 Storage of study documents	30
13 REFERENCES	31
APPENDIX I: PATIENT INFORMATION	32
APPENDIX II: INFORMED CONSENT FORM	37
APPENDIX III: DISTRESS (QUALITY OF LIFE) ASSESSMENT	40
APPENDIX IV: PERFORMANCE STATUS (ECOG)	41
APPENDIX V: ETHICS COMMITTEE VOTE	42
APPENDIX VI: INSURANCE	43

1A Synopsis (English version)

Study title	High-precision radiotherapy of motor deficits due to metastatic spinal cord compression
Study designation	PRE-MODE
Sponsor	University Hospital Schleswig-Holstein, Campus Lübeck
Coordinating Investigator	[name]. [name], Department of Radiation Oncology, University of Lübeck & University Hospital Schleswig-Holstein, Campus Lübeck, Germany
Study start	January 2017
Study period	30 months: recruitment = 18 months, follow up = 6 months, analyses, reporting and publication = 6 months
Type of protocol	Multinational phase 2 multi-center study (single arm) supplemented by a comparison to a historical, propensity score matched control group (superiority study)
Indication	Motor deficits of the lower extremities due to metastatic spinal cord compression (MSCC)
Rationale	For MSCC, conventional radiotherapy (RT) with 10x3 Gy in 2 weeks results in similar motor function but better local progression-free survival (LPFS) than conventional RT with 5x4 Gy in 1 week. Since patients with MSCC are often significantly impaired, a RT regimen with an overall treatment time of only 1 week would be preferable if it resulted in similar LPFS as 10x3 Gy in 2 weeks. This may be achieved with 5x5 Gy in 1 week, since the equivalent dose in 2 Gy fractions (EQD2) with respect to tumor cell kill of 5x5 Gy and 10x3 Gy are similar. Taking into account the tolerance dose of the spinal cord, 5x5 Gy can be safely administered with high-precision RT such as volumetric modulated arc therapy (VMAT) or stereotactic body radiotherapy (SBRT). This phase 2 study investigates LPFS after high-precision RT with 5x5 Gy in 1 week. The patients of the phase 2 study will be compared for LPFS to a historical control group receiving conventional RT with 5x4 Gy in 1 week. If superiority regarding LPFS is shown for high-precision RT with 5x5 Gy, patients with MSCC would benefit from this regimen, since high LPFS rates can be achieved with an RT regimen of only 1 week (5x5 Gy) instead of 2 weeks (10x3 Gy).
Treatment	Study arm: 5x5 Gy of high-precision RT in 1 week Historical control: 5x4 Gy of conventional RT in 1 week Follow-up directly and at 1, 3 and 6 months following RT
Primary endpoint	LPFS at 6 months following RT
Secondary endpoints	1. Motor function/Ability to walk Assessment directly and at 1, 3 and 6 months following RT

	
2. Sensory function Assessment directly and at 1, 3 and 6 months following RT
 
3. Sphincter dysfunction Assessment directly and at 1, 3 and 6 months following RT
 
4. Local progression-free survival Additional evaluation directly and 1 and 3 months following RT
 
5. Overall survival Evaluation directly and at 1, 3 and 6 months following RT
 
6. Pain Evaluation directly and at 1, 3 and 6 months following RT
 
7. Distress (as an indicator of quality of life) Evaluation directly and at 1, 3 and 6 months following RT
 
8. Toxicity Evaluation during plus directly, 1, 3 and 6 months following RT

Number of patients	44 patients (phase 2 study)
Inclusion criteria	
 1. Motor deficits of the lower extremities resulting from MSCC, which have persisted for no longer than 30 days 2. Confirmation of diagnosis by magnetic resonance (MR) imaging (computed tomography (CT) allowed) 3. Age 18 years or older 4. Written informed consent 5. Capacity of the patient to contract
Exclusion criteria	
 1. Previous RT or surgery of the spinal areas affected MSCC 2. Symptomatic brain tumor or symptomatic brain metastases 3. Metastases of the cervical spine only 4. Other severe neurological disorders 5. Pregnancy, lactation period 6. Indication for decompressive surgery of affected spinal areas
Statistics/Sample size calculation	
The primary endpoint of this phase 2 study is to assess high-precision RT with 5x5 Gy in 1 week with respect to 6-month LPFS and to demonstrate that this rate is superior to conventional RT with 5x4 Gy (hypothesis).
 
To ensure with 80% power that – in the phase 2 study- the 95% confidence interval for the true 6-month LPFS rate has a precision of +/-20% a total of 44 patients should be enrolled. For comparison of the prospective study results with historical controls, a propensity score approach will be applied to account for baseline differences between treatment arms to balance covariates and remove bias that may arise due to these confounders. Ten relevant prognostic factors will be included. Assuming that roughly 400 historical controls qualify for this comparison, a power of at least 80% will be ensured assuming that the true 6-month LPFS rate with conventional RT with 5x4 Gy is roughly 67% and a 20% percentage increase is considered as clinically relevant.

End of study	The study is completed when all patients have either died or been followed for at least 6 months and analyses, reporting and publication have been finished, or when the study has been terminated due to other reasons (for example patient safety).

PRE-MODE

Flow Chart

	Prior to RT	End of RT	Follow up at 1 month (+/- 2 weeks) following RT	Follow up at 3 months (+/- 2 weeks) following RT	Follow up at 6 months (+/- 2 weeks) following RT
Informed Consent	X				
Medical History/Concomitant Diseases	X				
Prognostic factors	X				
Physical examination	X	X	X	X	X
Inclusion/Exclusion Criteria	X				
Motor Function	X	X	X	X	X
Sensory Function	X	X	X	X	X
Sphincter Dysfunction	X	X	X	X	X
Ambulatory Status	X	X	X	X	X
Pain	X	X	X	X	X
Distress (quality of life)	X	X	X	X	X
Toxicity*	X	X	X	X	X
LPFS		X*	X	X	X
Overall survival		X*	X	X	X

*also during RT

1B Synopsis (German version)

Studientitel	Hochpräzisions-Strahlentherapie bei motorischen Defiziten aufgrund metastatisch bedingter Rückenmarkskompression
Studienbezeichnung	PRE-MODE
Sponsor	Universitätsklinikum Schleswig-Holstein, Campus Lübeck
Studienleiter	[name]. [name] Klinik für Strahlentherapie Universität zu Lübeck & Universitätsklinikum Schleswig-Holstein, Campus Lübeck, Deutschland
Studienstart	Januar 2017
Studiendauer	30 Monate: Rekrutierung = 18 Monate, Follow up = 6 Monate, Analysen, Berichte und Publikation = 6 Monate
Art des Protokolls	Multinationale Phase 2 Multicenter-Studie (einarmig), ergänzt durch den Vergleich mit einer historischen Kontrollgruppe mittels Propensity Score Matching (Überlegenheitsstudie)
Indikation	Motorische Defizite der unteren Extremitäten aufgrund einer metastatisch bedingten Rückenmarkskompression
Rationale	Bei der metastatisch bedingten Rückenmarkskompression (MSCC) führt die konventionelle Bestrahlung mit 10x3 Gy in 2 Wochen zu ähnlicher motorischer Funktion aber zu einem besseren lokalen progressionsfreien Überleben (LPFS) als eine konventionelle Bestrahlung mit 5x4 Gy in 1 Woche. Da Patienten mit MSCC oft deutlich beeinträchtigt sind, wäre eine Strahlentherapie mit einer Gesamtbehandlungszeit von nur einer Woche zu bevorzugen, wenn diese zu einem ähnlichen LPFS führen würde wie 10x3 Gy in 2 Wochen. Dies könnte mit 5x5 Gy in 1 Woche erreicht werden, da die EQD2s von 5x5 Gy und 10x3 Gy hinsichtlich Tumorzellvernichtung ähnlich sind. Wenn man die Toleranzdosis des Rückenmarks berücksichtigt, kann das Regime 5x5 Gy sicher mit einer Hochpräzisions-Strahlentherapie (VMAT oder SBRT) verabreicht werden. Darum untersucht diese Phase 2 Studie die LPFS nach Hochpräzisions-Strahlentherapie mit 5x5 Gy in 1 Woche. Die Patienten/innen der Phase 2 Studie werden hinsichtlich LPFS mit einer historischen Kontrollgruppe verglichen, die eine konventionelle Bestrahlung mit 5x4 Gy in 1 Woche erhalten hat. Kann eine Überlegenheit der Hochpräzisions-Strahlentherapie mit 5x5 Gy gezeigt werden, würden Patienten mit MSCC von diesem Regime profitieren, da sie eine hohe LPFS-Rate mit einem Regime erreichen können, das nur 1 Woche (5x5 Gy) statt 2 Wochen (10x3 Gy) dauert.
Behandlung	Studienarm: Hochpräzisions-Strahlentherapie mit 5x5 Gy in 1 Woche

	
Historische Kontrollgruppe:
 
konventionelle Strahlentherapie mit 5x4 Gy in 1 Woche
 
Nachuntersuchungen direkt sowie 1, 3 und 6 Monate nach Strahlentherapie

Primärer Endpunkt	LPFS 6 Monate nach Strahlentherapie
Sekundäre Endpunkte	
1. Motorische Funktion / Gehfähigkeit Beurteilung direkt sowie 1, 3 und 6 Monate nach Strahlentherapie
 
2. Sensibilität Beurteilung direkt sowie 1, 3 und 6 Monate nach Strahlentherapie
 
3. Blasen-Mastdarm-Störungen Beurteilung direkt sowie 1, 3 und 6 Monate nach Strahlentherapie
 
4. Lokales progressionsfreies Überleben Zusätzliche Beurteilung direkt sowie 1 und 3 Monate nach Strahlentherapie
 
5. Gesamtüberleben Beurteilung direkt sowie 1, 3 und 6 Monate nach Strahlentherapie
 
6. Schmerz Beurteilung direkt sowie 1, 3 und 6 Monate nach Strahlentherapie
 
7. Distress (als Indikator für Lebensqualität) Beurteilung direkt sowie 1, 3 und 6 Monate nach Strahlentherapie
 
8. Toxizität Beurteilung während sowie direkt, 1, 3 und 6 Monate nach Strahlentherapie

Anzahl der Patienten	44 Patienten (Phase 2 Studie)
Einschlußkriterien	
 1. Motorische Defizite der unteren Extremitäten als Ergebnis einer metastatisch bedingten Rückenmarkskompression welche nicht länger als 30 Tage bestanden hat 2. Bestätigung der Diagnose mittels Kernspintomographie (CT genehmigt) 3. Alter 18 Jahre oder älter 4. Schriftliche Einverständniserklärung 5. Geschäftsfähigkeit des Patienten/der Patientin
Ausschlußkriterien	
 1. Frühere Strahlentherapie oder Operation der von der metastatisch bedingte Rückenmarkskompression betroffenen Wirbelsäulenregionen 2. Symptomatischer Hirntumor oder symptomatische Hirnmetastasen 3. Ausschließlich Metastasen der Halswirbelsäule 4. Andere schwere neurologische Erkrankungen 5. Schwangerschaft, Stillzeit 6. Indikation für eine Dekompressions-Operation der betroffenen Wirbelsäulenregionen
Statistik/Fallzahl-Berechnung	Der primäre Endpunkt dieser Phase 2 Studie beinhaltet die Erfassung der LPFS-Rate nach 6 Monaten nach Hochpräzisions-Strahlentherapie mit 5x5 Gy in 1 Woche sowie den Nachweis, dass diese Rate höher ist als nach konventioneller Strahlentherapie mit 5x4 Gy (Hypothese).

PRE-MODE

	
Um mit einer statistischen Power von 80% zu gewährleisten, dass in dieser Phase 2 Studie das 95%-Konfidenzintervall für die wahre LPFS-Rate nach 6 Monaten eine Genauigkeit von +/-20% aufweist, müssen 44 Patienten/innen eingeschlossen werden. Für den Vergleich mit der historischen Kontrollgruppe wird ein Propensity Score Matching durchgeführt, um Unterschiede zwischen beiden Gruppen hinsichtlich Patientencharakteristika und Kovariablen auszugleichen und eine durch mögliche Unterschiede resultierende Verzerrung (Bias) zu vermeiden. Zehn relevante Prognosefaktoren werden hierbei berücksichtigt. Unter der Annahme, dass sich ungefähr 400 Patienten/innen für die historische Kontrollgruppe qualifizieren, wird eine statistische Power von 80% erreicht, wobei davon ausgegangen wird, dass die wahre LPFS-Rate 6 Monate nach konventioneller Strahlentherapie mit 5x4 Gy 67% beträgt und eine Verbesserung von absolut 20% als klinisch relevant angesehen wird.

Ende der Studie	
Die Studie ist abgeschlossen, wenn alle Patienten entweder verstorben sind oder für wenigstens 6 Monate nachbeobachtet wurden und Analysen, Berichte und die Publikation abgeschlossen sind oder die Studie aus anderen Gründen beendet wurde (zum Beispiel Patientensicherheit).

Ablaufplan

	Vor Strahlentherapie	Am Ende der Strahlentherapie	1 Monat (+/- 2 Wochen) nach Strahlentherapie	3 Monate (+/- 2 Wochen) nach Strahlentherapie	6 Monate (+/- 2 Wochen) nach Strahlentherapie
Einverständniserklärung	X				
Anamnese/Begleiterkrankungen	X				
Prognosefaktoren	X				
Ärztliche Untersuchung	X	X	X	X	X
Ein-/Ausschlusskriterien	X				
Motorische Funktion	X	X	X	X	X
Sensibilität	X	X	X	X	X
Blasen-Mastdarm-Störungen	X	X	X	X	X
Gehfähigkeit	X	X	X	X	X
Schmerz	X	X	X	X	X
Distress (Lebensqualität)	X	X	X	X	X
Toxizität*	X	X	X	X	X
LPFS		X*	X	X	X
Gesamt Überleben		X*	X	X	X

*ebenfalls während der Strahlentherapie

2 List of Abbreviations

AE	adverse event
ASIA	American Spinal Injury Association
GCP	good clinical practice
CR	complete response
CRF	case report form
CT	computed tomography
CTCAE	Common Terminology Criteria for Adverse Events
DEGRO	German Society for Radiation Oncology
ECOG	Eastern Cooperative Oncology Group
EQD2	equivalent dose in 2 Gy fractions
LPFS	local progression-free survival
MR	magnetic resonance
MSCC	metastatic spinal cord compression
OS	overall survival
PR	partial response
PTV	planning target volume
QUANTEC	Quantitative Analyses of Normal Tissue Effects in the Clinic
RT	radiotherapy
SAE	serious adverse event
SBRT	stereotactic body radiotherapy
UAE	unexpected adverse events
UKSH	University Hospital Schleswig-Holstein
VMAT	volumetric modulated arc therapy

3 Background and Rationale

3.1 Background

Metastatic spinal cord compression (MSCC) occurs in 5-10% of all cancer patients during the course of their disease [1, 2]. Radiotherapy (RT) alone is the most common treatment. However, the most appropriate radiation schedule is still a matter of debate. The survival prognosis of many patients with MSCC is poor measured in months [1-3]. Every radiotherapy session may be associated with discomfort for the often significantly impaired patients in a palliative situation, in particular regarding the transport to the radiotherapy department and the patient's positioning on the treatment couch. Thus, a more patient convenient radiation schedule with a short overall treatment time (short-course radiotherapy such as 5x4 Gy in 1 week) would be preferable if it was as effective as the most commonly used radiation schedule for MSCC, 10x3 Gy in 2 weeks. Both retrospective and prospective studies have shown that 5x4 Gy in 1 week and 10x3 Gy in 2 weeks are similarly effective with respect to their effect on motor function [3, 4].

However, a prospective non-randomized study has demonstrated that longer-course radiotherapy programs such as 10x3 Gy in 2 weeks resulted in better local progression-free survival (LPFS) than short-course programs such as 5x4 Gy in 1 week [5]. LPFS was defined as freedom from progression of motor deficits during RT and freedom from an in-field recurrence of MSCC (i.e. freedom from motor deficits due to a recurrence of MSCC in the previously irradiated parts of the spine) following RT. In that study, which compared longer-course to short-course radiotherapy, the vast majority of the patients in the longer-course RT group had received 10x3 Gy and the vast majority of patients in the short-course RT group 5x4 Gy [5]. The LPFS at 6 months were 86% after longer-course RT and 67% after short-course RT, respectively ($p=0.034$). Local progression of MSCC is a serious situation, since spinal surgery or a second course of radiotherapy in the same area of the spinal cord may not be possible. Therefore, such a progression must be avoided.

The ideal RT schedule for MSCC would be both short and effective in improving LPFS. The biological effect of radiotherapy depends on both the total dose and the dose per fraction [6]. The biologically effective doses of different RT schedules can be compared by calculating the equivalent dose in 2 Gy fractions (EQD2) [7]. The EQD2 with respect to tumor cell kill is 23.3 Gy for 5x4 Gy and 32.5 Gy for 10x3 Gy, respectively. RT of MSCC can be intensified with the use of high-precision techniques such as volumetric modulated arc therapy (VMAT) and stereotactic body radiotherapy (SBRT) considering the tolerance doses of the spinal cord and the vertebral bone [8-11]. The EQD2 of high-precision RT with 5x5 Gy in 1 week is 31.3 Gy, which is similar to the EQD2 of 10x3 Gy (32.5 Gy). Thus, with 5x5 Gy of high-precision RT in 1 week, one can expect similar LPFS as with 10x3 Gy in 2 weeks. The EQD2 of 5x5 Gy for radiation-related myelopathy is 43.8 Gy, which is below the tolerance dose of the spinal cord (45-50 Gy). The EQD2 of 5x5 Gy for damage to the vertebral bone is 41.7 Gy, which is well below the tolerance dose of bone (52 Gy) [9-11]. Therefore, high-precision RT with 5x5 Gy can be considered a safe treatment regarding the risk of radiation myelopathy and damage to the vertebral bone.

In contrast to other countries, decompressive surgery prior to RT has become increasingly popular for MSCC in Germany during the last 10 years, although it has been recommended only for selected patients [12-15]. Thus, the proportion of patients treated with RT alone for MSCC in Germany is decreasing, and a randomized, prospective clinical trial comparing 5x5 Gy of high-precision RT to 5x4 Gy of conventional RT with a sufficiently large sample size will be quite difficult to perform within a reasonable period of time. Therefore, the present study is designed as a single-arm phase 2 study. Subsequently, the patients of the phase 2 study will be compared to a historical control group. Propensity score matching will be performed to balance covariates and remove bias that may arise due to these confounders. Ten potential prognostic factors will be included. This design can be

PRE-MODE

considered appropriate to answer the question whether high-precision RT with 5x5 Gy results in significantly better LPFS than 5x4 Gy of conventional RT in patients irradiated for MSCC.

3.2. Rationale

In patients treated with RT alone for MSCC, conventional RT with 10x3 Gy in 2 weeks results in similar motor function but significantly better LPFS than conventional RT with 5x4 Gy in 1 week. Since patients with MSCC are often significantly impaired, a RT regimen with an overall treatment time of only 1 week would be preferable if it resulted in similar LPFS as 10x3 Gy in 2 weeks. This may be achieved with 5x5 Gy in 1 week, since the EQD2 with respect to tumor cell kill of 5x5 Gy and 10x3 Gy are similar. Taking into account the tolerance dose of the spinal cord, 5x5 Gy can be safely administered with high-precision RT such as VMAT (or SBRT). Therefore, the present phase 2 study investigates the LPFS after high-precision RT with 5x5 Gy in 1 week. To demonstrate superiority when compared to conventional RT with 5x4 Gy in 1 week, the patients of the phase 2 study will be compared to a historical control group receiving conventional with 5x4 Gy in 1 week. If superiority regarding LPFS can be shown for high-precision RT with 5x5 Gy, patients with MSCC would benefit from this regimen, since they can achieve high LPFS rates with an RT regimen lasting only 1 week (5x5 Gy) instead of 2 weeks (10x3 Gy). This study aims to make a significant contribution to the most appropriate RT schedule for patients with MSCC.

4 Endpoints

4.1. Primary endpoint

The primary aim of this study is to investigate the LPFS of MSCC after 5x5 Gy of high-precision RT (VMAT = preferred technique, SBRT = allowed for patients with involvement of only one vertebra, if the required constraints [please see 6.2.1] can be met) and to demonstrate that this regimen results in significantly better 6-month LPFS than conventional RT with 5x4 Gy. LPFS is defined as freedom from progression of motor deficits during RT and freedom from an in-field recurrence of MSCC (i.e. freedom from motor deficits due to a recurrence of MSCC in the previously irradiated parts of the spine) following RT. The LPFS rate will be assessed 6 months after the end of RT.

4.2. Criteria for secondary endpoints

In addition, the following endpoints will be evaluated:

1. Motor function/Ability to walk: Assessment directly and at 1, 3 and 6 months after RT
2. Sensory function: Assessment directly and at 1, 3 and 6 months after RT
3. Sphincter dysfunction: Assessment directly and at 1, 3 and 6 months after RT
4. Local progression-free survival: Additional evaluation directly and at 1, 3 and 6 months after RT
5. Overall survival: Evaluation directly and at 1, 3 and 6 months after RT
6. Pain: Evaluation directly and at 1, 3 and 6 months after RT
7. Distress: Evaluation directly and at 1, 3 and 6 months after RT
8. Toxicity: Evaluation during RT, and directly, 1, 3 and 6 months after RT

5 Study Design and Patient Selection

5.1 General design and duration

This is a single-arm study, which will investigate the effect of high-precision RT with 5x5 Gy on LPFS in patients irradiated for MSCC.

The recruitment of all 44 patients (40 patients + 10% for potential drop-outs) should be completed within 18 months. The follow-up period will be 6 months. Another 6 months are required for analyses, reporting and publication. This equals a total running time for the study of 30 months.

In accordance with a previous study assessing local control of MSCC, the following patient characteristics will be recorded to allow adequate comparison with the historical, propensity-score matched control group [16]:

- Age (2 groups, depending on median age)
- Gender
- Type of primary tumor (breast cancer vs. prostate cancer vs. myeloma/lymphoma vs. lung cancer vs. other tumors)
- Interval from tumor diagnosis to MSCC (≤ 15 months vs. > 15 months)
- Number of involved vertebrae (1-2 vs. ≥ 3)
- Other bone metastases at the time of RT (no vs. yes)
- Visceral metastases at the time of RT (no vs. yes)
- Time developing motor deficits prior to RT (1-7 days vs. 8-14 days vs. > 14 days)
- Ambulatory status prior to RT (no vs. yes)
- Eastern Cooperative Oncology Group (ECOG) performance score (1-2 vs. 3-4)

5.2 Patient selection

5.2.1 General prerequisites

Patients have to be adequately informed about their diagnosis and about the nature, significance and scope of the study. Patients may only be included after completing the pre-therapy clarification and on fulfilment of all inclusion criteria and on non-fulfilment of all exclusion criteria. Prior to inclusion in the study, it should be clear that the patient is no clear candidate for decompressive surgery of the parts of the spinal cord involved by MSCC.

5.2.2 Inclusion and exclusion criteria

Inclusion criteria	
 1. Motor deficits of the lower extremities resulting from MSCC*, which have persisted for no longer than 30 days 2. Confirmation of diagnosis by MR-imaging (CT allowed) 3. Age 18 years or older 4. Written informed consent 5. Capacity of the patient to contract
Exclusion criteria	
 1. Previous RT or surgery of the spinal areas affected MSCC 2. Symptomatic brain tumor or symptomatic brain metastases 3. Metastases of the cervical spine only 4. Other severe neurological disorders 5. Pregnancy, Lactation 6. Indication for decompressive surgery of affected spinal areas

*MSCC may affect single or multiple spinal sites

5.2.3 Termination criteria for individual patients

The patient may terminate participation in the study at any time and without giving any reasons. Otherwise, the reasons for terminating participation in the study are the same as those for individually breaking off treatment with radiotherapy.

- Serious adverse event (SAE), which necessitates termination of treatment
- Unacceptable toxicities
- Pregnancy

Date and reason for termination of treatment have to be documented, if indicated by the patient.

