5.2.5 Definition of the end of the study

The study is completed when all patients have either died or been followed up for at least 6 months, or the study has been terminated.

The patient will continue to receive treatment at the clinic in question after the 6-month follow-up period, or the premature termination of the study for the patient.

6 Treatment

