6.2.3. Possible side effects of high-precision RT

High-precision RT in the thoracic spinal area may be associated with nausea and vomiting, whereas RT in the lumbar spine may be associated with diarrhea. In case of grade 3 toxicity according to Common Terminology Criteria for Adverse Events (CTCAE), RT may be delayed for a maximum of 7 days. If the symptoms persist, RT will be terminated. If RT has to be terminated, the head of the clinical study has to be informed.

7 Safety Management

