7.3 Reporting of adverse events

SAEs and UAEs must be reported within 24 hours after their detection/onset by fax to the address below (see separate document attached to the case report form):

[name]. [name]

*Klinik für Strahlentherapie, Universität zu Lübeck
[name]*

[contact]

[contact]

Email: [contact]

8 Assessments

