8.3.4 Overall survival

Overall survival (OS) time will be calculated for each patient from the last day of radiotherapy up to 6 months following RT. Patients will be followed up until death or for at least 6 months.

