8.3.7 Toxicity

Toxicity will be assessed according to CTCAE 4.03 during RT, directly after RT and at 1, 3 and 6 months following RT [20]. If radiation myelopathy is suspected (i.e. deterioration according to the modified ASIA scale [19]), spinal MR-imaging will be performed.

9 Comparisons to Historical Control Group

The patients of this study who received high-precision RT with 5x5 Gy for MSCC will be matched to historical control group treated with 5x4 Gy of conventional RT between 2001 and 2016. This data set consists of 680 patients.

The patients of the control group are part of an already existing anonymized database. To be eligible for control group, patients fulfilling the same inclusion criteria and exclusion criteria as defined in the prospective phase II study are considered. Furthermore, to be consistent with efficacy analysis of phase II study, patients of the historical control group must have received at least 80% of the planned RT dose. This will lead to more than 600 patients qualifying for the comparison with the prospectively collected phase 2 data.

For comparison purposes, a propensity score approach will be applied to account for baseline differences between treatment arms to balance covariates and remove bias that may arise due to these confounders. A propensity score is a conditional probability of assignment to a particular treatment given a number of baseline covariates. Except for unmeasured potential confounding factors, patients having the same propensity score but assigned to different treatments will tend to have the same (or nearly the same) distributions on their background covariates and thus are considered to be similar to random assignment of treatments. To estimate the odds of receiving a specific radiotherapy a non-parsimonious multivariable logistic regression model will be estimated. Covariates to be included in the model will be the following ten prognostic factors [16]:

- Age (2 groups, depending on median age)
- Gender
- Type of primary tumor (breast cancer vs. prostate cancer vs. myeloma/lymphoma vs. lung cancer vs. other tumors)
- Interval from tumor diagnosis to MSCC (≤ 15 vs. > 15 months)
- Number of involved vertebrae (1-2 vs. ≥ 3)
- Other bone metastases at the time of RT (no vs. yes)
- Visceral metastases at the time of RT (no vs. yes)
- Time developing motor deficits prior to RT (1-7 days vs. 8-14 days vs. > 14 days)
- Ambulatory status prior to RT (no vs. yes)

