10.2. Statistical analyses

10.2.1 Primary endpoint:

The primary endpoint (LPFS of MSCC) will be evaluated based on the sample size calculations described above. The evaluation will be performed in those patients, who are available for assessment of the primary endpoint and have received at least 80% of the planned RT dose. Due to the open nature of the study, a blind data review is not necessary. The safety population includes all patients who have received at least 1 fraction of high-precision RT.

LPFS is defined as freedom from progression of motor deficits during RT and freedom from an in-field recurrence of MSCC (i.e. freedom from motor deficits due to a recurrence of MSCC in the previously irradiated parts of the spine) following RT [5]. Deterioration of motor deficits during RT will be counted as LPFS of 0 months. Freedom from an in-field recurrence following RT will be referenced from the last day of RT. To investigate clinically important, sustainable effects of precision radiotherapy and avoid over-evaluation of early temporal shifts without any longer term relevance, study design and analysis focuses on binary endpoints evaluated at 6-months rather than time-to-event analyses.

10.2.2 Secondary endpoints:

Secondary endpoints:

An improvement or deterioration of the motor function will be defined as a change of at least 1 point on a 5-point scale [17]. Effect of RT on motor function and post-RT ambulatory rates will be evaluated directly after RT and at 1, 3 and 6 months following RT in those patients who are alive and available for assessment. To investigate whether propensity scores removed bias due to differences in covariates between studies and to compare binary study endpoints after stratification of patients by propensity scores Cochran-Mantel-Haenszel tests were performed. P-values of <0.05 are considered significant.

Overall survival (OS) will be counted from the last day of RT. To investigate clinically important, sustainable effects of precision radiotherapy and avoid over-evaluation of early temporal shifts without any longer term relevance, study design and analysis focuses on binary endpoints evaluated at 6-months rather than time-to-event analyses. The analysis of OS will be conducted in the intent-to-treat population.

Data regarding sensory deficits, sphincter dysfunction, pain, distress and toxicity will only be assessed in the phase 2 study.

11 Ethical and Legal Principles

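### Section 5.2.3 ties leaving the study to stopping radiotherapy, which conflicts with the 6-month follow-up, safety and survival analyses required elsewhere and could cost later data in patients selected by toxicity

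*Combined protocol and SAP*

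**What the plan says.** Section 5.2.3 first allows withdrawal by the patient at any time. It then continues: "Otherwise, the reasons for terminating participation in the study are the same as those for individually breaking off treatment with radiotherapy", and lists an SAE that requires treatment to end, unacceptable toxicities, and pregnancy. Section 5.2.5 says the patient goes on being treated at the clinic "after the 6-month follow-up period, or the premature termination of the study for the patient", so an individual exit before 6 months is foreseen. Section 6.2.3, after a delay for grade 3 toxicity, says "If the symptoms persist, RT will be terminated" and asks that the head of the study be told. It is silent on visits afterwards.

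Other sections assume complete follow-up. Section 8.3.4: "Patients will be followed up until death or for at least 6 months". Section 8.3.7: "Toxicity will be assessed according to CTCAE 4.03 during RT, directly after RT and at 1, 3 and 6 months following RT". Section 10.2.1: "The safety population includes all patients who have received at least 1 fraction of high-precision RT". Section 10.2.2 analyses overall survival by intention to treat, as a binary outcome at 6 months. Section 7.3 covers the event itself: "SAEs and UAEs must be reported within 24 hours after their detection/onset by fax".

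**The concern.** Ending treatment and ending observation are separate decisions, and 5.2.3 gives them the same triggers. A site that follows it to the letter would not hold the remaining 1-, 3- and 6-month visits for a patient whose RT was stopped for toxicity. The exit is then triggered by something close to the outcomes being measured, so the missing data are plausibly informative. Defining the analysis sets broadly does not help, because an intention-to-treat set cannot supply a vital status that nobody collected.

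Three features of the plan add to the exposure:

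- Survival is a 6-month yes/no outcome, so there is no censoring to accommodate an early exit, and no rule says how unknown status counts.
- Section 9 compares survival with historical controls. No section applies the 5.2.3 exit rule to them, so any loss could fall on the study arm alone.
- The primary endpoint is touched at the margin. A patient stopped after 4 of 5 fractions has had 20/25 = 80% of the dose and meets the threshold in 10.2.1, but must also be available for assessment.

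**Working it through.** **1. The plan's own figure.** Section 5.1 gives 44 patients as 40 plus 10%: 40 × 1.10 = 44. (Dividing instead, 40/0.90 = 44.4, gives 45; nothing here depends on the difference.) The allowance is 44 − 40 = 4 patients. Section 10.1 says it covers early loss to follow-up and premature discontinuation of RT together, and concerns eligibility for the efficacy analysis. It is not an estimate of how many stop for toxicity. I use 4 as an illustration, with 1 and 2 for comparison.

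**2. The sections side by side, for a patient whose RT is stopped for toxicity.**

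| Data | 5.2.3 read literally | Elsewhere |
|---|---|---|
| Toxicity or SAE that stops RT | recorded | recorded (7.3, 8.3.7) |
| Toxicity at 1, 3, 6 months | not collected | required (8.3.7) |
| Motor function at 1, 3, 6 months | not collected | scheduled (8.1, 8.3.2) |
| Vital status at 6 months | not collected | required (8.3.4), needed for 10.2.2 |

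No section says expressly that such a patient stays on the visit schedule.

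**3. Survival at 6 months.** Let m of 44 leave with unknown status and let p be survival among the 44 − m who stay. The documents give no survival rate, so p = 30%, 50% and 70% are assumptions. Assume also that patients with unknown status are left out, so the reported rate is p.

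- If all who leave have died, the true rate is p(44 − m)/44, and the report is too high by p × m/44.
- If all who leave are alive, the true rate is [p(44 − m) + m]/44, and the report is too low by (1 − p) × m/44.

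For m = 4:

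| Reported p | All 4 dead | Error | All 4 alive | Error |
|---|---|---|---|---|
| 30% | 12/44 = 27.3% | +2.7 points | 16/44 = 36.4% | −6.4 points |
| 50% | 20/44 = 45.5% | +4.5 points | 24/44 = 54.5% | −4.5 points |
| 70% | 28/44 = 63.6% | +6.4 points | 32/44 = 72.7% | −2.7 points |

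The largest overstatement is 1.4 to 3.2 points for m = 2 and 0.7 to 1.6 points for m = 1.

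**4. Late toxicity.** Assume 5%, 10% or 20% of the 40 who stay have a late event, that is 2, 4 or 8 patients. With all 44 in the denominator and the 4 who left counted as event-free, the rates are 2/44 = 4.5%, 4/44 = 9.1% and 8/44 = 18.2%. If all 4 in fact had a late event, they are 6/44 = 13.6%, 8/44 = 18.2% and 12/44 = 27.3%. The gap is 4/44 = 9.1 points in each case. It is the most that the treatment of 4 unknowns can move the result.

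**The case against.** The case for reading the plan more kindly is substantial. Sections 8.3.4 and 10.2 carry no exception for stopped RT. The first sentence of 5.2.5 makes completion of the study depend on every patient having died or reached 6 months, unless the study itself is terminated. The phrase "or the premature termination of the study for the patient" fits a patient who withdraws voluntarily just as well. Nothing instructs a site to close the record, and the last line of 5.2.3 asks only for the date and reason for ending treatment. Loss of follow-up is therefore one side of a contradiction and not a settled outcome.

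The trigger is also not lost, since toxicity is assessed during and directly after RT and SAEs are reported within 24 hours. The direction of any bias is open too. A patient stopped after 2 fractions has had 2/5 of the 43.8 Gy EQD2 given for myelopathy, about 17.5 Gy, so is not obviously the patient whose absence hides late cord damage. The side effects named in 6.2.3 are nausea, vomiting and diarrhea, and no section predicts that they last to 6 months. Few patients may stop a one-week, five-fraction course.

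All of this stands as a limit on how much may be claimed. It does not remove the conflict. Section 5.2.3 is the section on individual termination, it speaks of participation and not only of treatment, and no other section overrides it in terms.

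**Conclusion.** The protocol gives sites conflicting instructions on whether to follow patients whose RT is stopped for an SAE or toxicity. If 5.2.3 prevails, later toxicity, motor function and 6-month vital status are missing in a group selected by toxicity, and late toxicity and binary 6-month survival may be biased. With 4 of 44 leaving, the survival error runs from 2.7 to 6.4 points in either direction, depending on whether those who leave are dead or alive. That rests on assumed survival of 30-70% among those who stay and on leaving unknowns out. The actual number is not given and may be smaller.

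A reader might infer that the patients harmed most do leave, and that toxicity and survival therefore look better than they are. The documents do not support that: other sections require the follow-up, the stopping event is captured, and the survival error can go either way. A reader might also set 0 of 40 with severe toxicity at 6 months against a true 4 of 44 (9.1%). That contrast needs the whole mixed 10% allowance to be toxicity stoppers, all of them affected at 6 months and nobody else affected. It also uses 40 as the denominator where 10.2.1 uses every treated patient.

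This is a worthwhile, inexpensive correction that mainly concerns secondary endpoints. The trial's main result does not hinge on it.

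**What to change.** - In 5.2.3, separate the end of RT from the end of study participation. State that stopping RT does not end follow-up, and that the assessments already scheduled at 1, 3 and 6 months, with vital status, continue unless the patient withdraws consent.
- Reconcile 5.2.3 and 5.2.5 with 8.3.4, 8.3.7 and 10.2.
- In 10.2, state how a patient with unknown 6-month status counts for survival and toxicity. This is needed even after the first change, for patients who withdraw or are lost. Report the best-case and worst-case counts alongside.
- Leave the clinical criteria for stopping RT as they are.

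The cost is a few sentences. Sample size and power are unaffected. The downside is a few visits, already in the schedule, for debilitated patients; a status report from the treating clinic could replace some of them. The change should be made before follow-up begins, because missed visits may not be recoverable.
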